4.2 Definition of diseases involved in the research

- 1) Hypertension is defined as: When blood pressure was measured on different days without antihypertensive drugs, patients had systolic blood pressure ≥ 140 mmHg and/or diastolic blood pressure ≥ 90 mmHg; Or patients with a history of hypertension who are currently taking antihypertensive medications and whose blood pressure is less than 140/90 MMHG are also diagnosed with hypertension. (For patients with newly diagnosed hypertension, it is recommended to return to the clinic and register after diagnosis. If there is no follow-up after the initial visit, registration will not be granted).
- 2) Diabetes is defined as: There are diabetes symptoms such as polydipsia, polyuria, polyphagia, and weight loss plus random blood glucose ≥ 11.1 mmol/L.. Fasting blood

glucose is ≥ 7.0 mmol/L; blood glucose is ≥ 11.1 mmol/L in 2 hours oral glucose tolerance test. Patient with a history of diabetes and is currently using hypoglycemic drugs should be considered diabetes even their blood sugar is normal.

3) Hyperlipidemia is defined as: In the absence of lipid-lowering drugs, for fasting measurement of blood lipids, total cholesterol is ≥ 6.2 mmol/L or low-density lipoprotein is ≥ 4.1 mmol/L or triglyceride is ≥ 2.3 mmol/L. Patient with a history of hyperlipidemia and is currently using lipid lowering drugs should be considered hyperlipidemia even their blood lipid is at a normal level

4) Coronary heart disease is defined as: Any history of myocardial infarction, coronary artery bypass grafting, coronary intervention, or coronary artery stenosis $>50\%$, or typical angina symptoms, and evidence of myocardial ischemia on electrocardiogram or echocardiography segmental wall motion abnormalities.

5) Heart failure is defined as: typical symptoms and signs of heart failure such as nocturnal paroxysmal dyspnea, reduced exercise tolerance, bilateral ankle joint edema, and left ventricular ejection fraction $<40\%$; or there are typical symptoms and signs of heart failure, left ventricular ejection fraction $\geq 40\%$, elevated BNP, left ventricular hypertrophy/left atrial enlargement or abnormal ventricular diastolic function; or a history of heart failure in the past, currently taking heart failure-related drugs, although there are no symptoms and signs of heart failure and laboratory findings, still diagnosed as heart failure.

6) Atrial fibrillation is defined as: single-lead electrocardiogram (≥ 30 s) or 12-lead electrocardiogram (≥ 10 s) shows that P wave disappears and is replaced by fibrillation

wave (f wave) with irregular size, shape and duration, the RR interval is absolutely irregular; or there is a history of atrial fibrillation in the past, and the drug related to atrial fibrillation is currently being taken. Although the electrocardiogram does not show the performance of atrial fibrillation, it is still diagnosed as atrial fibrillation.

7) Severe infection is defined as: life-threatening infection, including systemic inflammatory response syndrome, sepsis, septic shock or systemic multiple organ dysfunction syndrome.

8) Primary glomerular disease is defined as: a disease of unknown etiology, often involving bilateral glomeruli, with hematuria, proteinuria, edema, hypertension, renal dysfunction, etc. as the main clinical manifestations, including acute glomerulonephritis, rapidly progressive glomerulonephritis, chronic glomerulonephritis, asymptomatic hematuria and/or proteinuria, and nephrotic syndrome.

9) CSS score of cachexia is defined as: patients with CSS \geq 5 points are considered to be in the state of cachexia, referred to the "2020 Guidelines for the Clinical Diagnosis and Treatment of Cancer Cachexia", adopted the CSS Cachexia Staging Scale .

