3.7.1 Inclusion criteria

1. Age \geq 18 years old;
2. Diagnosed T2DM combined with \geq 1 CVD (hypertension, coronary heart disease, atrial fibrillation, heart failure);
3. During the data collection period, they went to the outpatient clinic of the cardiology department of the research center, or received treatment in the cardiology department;
4. Ability to self-sign informed consent (electronic /paper).

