6.4.2 Secondary endpoints

(1) Albuminuria level in patients with T2DM in the Department of Cardiology (microalbuminuria means UACR value >30 and <300 mg/g; macroalbuminuria means UACR value ≥ 300 mg/g);

(2) The prevalence and level of albuminuria in different types of cardiovascular diseases in the Department of Cardiovascular Medicine (microalbuminuria refers to UACR values >30 and <300 mg/g ; macroalbuminuria refers to UACR values ≥ 300 mg/g);

(3) Different treatment patterns for patients with CKD and patients without CKD;

(4) Assessing the current status of disease-related risk factor management in patients with T2DM attending cardiovascular medicine departments at different levels of hospitals;

(5) Evaluating the management of complications in patients with T2DM in different levels of hospitals.

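### The hypertension definition names treated patients only if their pressure is below 140/90, so treated patients at or above 140/90 fit neither branch without earlier off-drug readings

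*Protocol*

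**What the plan says.** Protocol section 4.2, item 1, gives two ways to be classified as hypertensive.

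- **Branch 1, readings off drugs:** "When blood pressure was measured on different days without antihypertensive drugs, patients had systolic blood pressure ≥ 140 mmHg", or a diastolic pressure of at least 90 mmHg. No time window is given.
- **Branch 2, treated patients:** those with a history "who are currently taking antihypertensive medications and whose blood pressure is less than 140/90 MMHG are also diagnosed with hypertension".

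The item also controls entry directly. A newly diagnosed patient who does not come back after the first visit is not to be registered.

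The next two items treat medicated patients differently. For diabetes: "Patient with a history of diabetes and is currently using hypoglycemic drugs should be considered diabetes even their blood sugar is normal". For hyperlipidemia, a patient with a history who is "currently using lipid lowering drugs should be considered hyperlipidemia even their blood lipid is at a normal level".

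Section 3.7.1 requires type 2 diabetes with at least one of "hypertension, coronary heart disease, atrial fibrillation, heart failure". Section 6.4.2 reports albuminuria by type of cardiovascular disease (endpoint 2) and lists "Assessing the current status of disease-related risk factor management in patients with T2DM" (endpoint 4). Section 6.3.1 includes disease history among the covariates. Section 4.1 has history of hypertension, medication and blood pressure recorded for every enrolled patient.

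**The concern.** Branch 2 joins its three conditions with a plain conjunction, so a pressure below 140/90 becomes a requirement. In the diabetes and hyperlipidemia items the normal value is only a concession. The group left unnamed is the one on drugs with pressure still at or above 140/90.

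Three things are at stake.

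- **Eligibility.** A patient with diabetes whose only cardiovascular disease is treated, uncontrolled hypertension can be ruled out by a site that follows the text.
- **Subgroup membership.** A similar patient who enters through coronary disease, atrial fibrillation or heart failure can be left out of the hypertension subgroup.
- **Consistency.** With 30 centers screening independently, some may apply the wording and others the evident intent.

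The loss may be related to the primary endpoint. Section 1.1 lists strict blood-pressure control among the measures for preventing kidney disease in diabetes, and section 6.3.1 uses blood pressure as a covariate for renal stage. Patients turned away would not appear in the central data. The screening form in Appendix 1 offers only refusal or failure to meet inclusion criteria as reasons, has no blood-pressure field, and under section 3.7 must stay at the sub-center.

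**Working it through.** **1. Classification by the text of item 1.** Raised pressure in an untreated patient is taken to have been found on different days. A treated patient is taken to have a history of hypertension.

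| Patient | Branch 1 read as current readings only | Branch 1 also met by earlier off-drug readings |
|---|---|---|
| Untreated, at or above 140/90 | hypertensive | hypertensive |
| Untreated, below 140/90 | not | only if such readings are on record |
| Treated, below 140/90 | hypertensive (branch 2) | hypertensive (branch 2) |
| Treated, at or above 140/90 | **not** | **only if such readings are on record** |

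**2. Would earlier readings be found?** Branch 1 is in the past tense with no time limit, so it allows them. No step asks for them, however. Section 4.1 collects data once. Section 5.2 queries recent tests over the last three months and names glucose, lipids, blood tests and renal function, not blood pressure. A long-treated patient would need readings from before treatment, on different days.

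**3. Possible effect on overall prevalence.** The protocol states no figure on this point, so the inputs are assumptions. Let s be the share of otherwise eligible patients who qualify only through treated, uncontrolled hypertension, and g the amount by which their albuminuria prevalence exceeds that of the rest. If all are excluded:

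fall in prevalence = s × g

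- s = 5%, g = 5 points: 0.05 × 5 = 0.25 points
- s = 10%, g = 10 points: 0.10 × 10 = 1.0 point
- s = 15%, g = 15 points: 0.15 × 15 = 2.25 points

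For scale, section 6.6 gives a 95% interval of 48.2% to 51.8% at 3,000 patients and 50% prevalence. This reproduces: 1.96 × √(0.25/3,000) = 1.79 points, so 48.21% to 51.79%, a half-width of about 1.8. The upper case exceeds that; the middle and lower cases do not. At a 15% share the gap must be more than 1.8/0.15 = 12 points to exceed it. Partial literal application reduces the fall in proportion.

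**4. Effect on a control rate computed on this label.** Let c be true control among treated hypertensives and q the share of treated, uncontrolled patients who qualify through earlier off-drug readings. Both are assumed.

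measured control = c / (c + (1 − c) × q)

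| c | q = 0 | q = 0.5 | q = 0.9 | q = 1 |
|---|---|---|---|---|
| 30% | 100% | 46.2% | 32.3% | 30% |
| 50% | 100% | 66.7% | 52.6% | 50% |
| 70% | 100% | 82.4% | 72.2% | 70% |

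Example: c = 50%, q = 0.5 gives 0.5/(0.5 + 0.5 × 0.5) = 66.7%. The rate is overstated whenever q is below 1, and reaches 100% only at q = 0.

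**The case against.** The best defence is that item 1 is clumsy wording, not an intended exclusion. Branch 2 reads as an extension to patients whose controlled pressure might hide the disease, and the parallel items on diabetes, hyperlipidemia, heart failure and atrial fibrillation all follow that pattern. Many cardiology sites would include a treated patient with high pressure without hesitation. This is persuasive about intent. It does not change the sentence that sites are asked to apply, and it supports rewording.

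A reader might also infer more than the text supports:

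- **That uncontrolled hypertension as a whole is not counted.** Untreated patients at or above 140/90 are counted in branch 1. Only the treated group is unnamed.
- **That control among treated hypertensives is 100% by construction.** This needs branch 1 to be restricted to current readings, which the text does not say.
- **That endpoint 4 becomes meaningless.** Section 6.4.2 defines no control rate and no denominator of labelled hypertensives. Control among enrolled patients can be computed from history, medication and blood pressure without the label.
- **That atrial fibrillation and heart failure have the same gap.** They do not. The atrial fibrillation item has a history route requiring that "the drug related to atrial fibrillation is currently being taken", but its electrocardiogram route carries no drug-free condition, so a treated patient with active disease qualifies. The heart failure item works likewise. A history without current drugs is a different matter.

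It is also true that the prevalence shift rests wholly on assumed inputs, and that patients with another qualifying disease enter the study anyway.

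**Conclusion.** The gap is real and narrow. As written, treated patients at or above 140/90 qualify as hypertensive only through earlier off-drug readings that the study does not seek. Literal use can exclude those with no other qualifying disease and misclassify those with one.

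The likely direction is a lower albuminuria prevalence. The size cannot be computed from the protocol: the range of 0.25 to 2.25 points holds only under the assumed shares and gaps, with every site reading the item literally and no affected patient rescued by old readings. Any control rate based on the label would be biased upward, by an amount that depends on how many such patients have those readings.

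This is most likely a drafting or translation fault. It is still worth correcting, because the subgroup label can be rebuilt for enrolled patients but patients screened out leave no trace in the central data.

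**What to change.** Reword branch 2 of section 4.2, item 1, to match items 2 and 3: a history of hypertension with current antihypertensive medication counts as hypertension even if the current pressure is below 140/90, that is, whatever the current reading. Send sites a short note so that all apply the same rule.

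Compute any blood-pressure control rate from the recorded history, medication and blood pressure, not from the section 4.2 label.

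The cost is one sentence, the note, and the ethics review or filing that section 8.2 requires for a protocol change. No new data are needed. The atrial fibrillation and heart failure items need no change on this account.

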4.3 Research procedure

The patient recruitment consisted of two parts, 50 patients from outpatients attending the Department of Cardiology and 50 from in patients receiving treatment in the Department of Cardiology.

- In the outpatient department, a selected, representative cardiologist should be followed and eligible patients among the physician's visits would be continuously screened. It is necessary to communicate with the person in charge of the Department of Cardiology

[figure not shown]
before the start of the branch center to determine the following outpatient doctors, and plan and determine the enrollment process with the outpatient doctors in advance. On the screening day, record and follow the T2DM patients encountered by the doctor during the consultation process, communicate with the patient for informed consent, screen according to the inclusion criteria, and generate a study number for those who meet the enrollment criteria (see flow chart 1).

- In the ward selected by the inpatient department of the Department of Cardiology, the clinical coordinator conducts a preliminary examination of all inpatients in the ward through the hospital medical record system, records the patient with T2DM, and communicates with the patient for informed consent, according to the inclusion and exclusion criteria, screening is carried out, and those who meet the inclusion conditions are enrolled and a research number is generated (see flow chart 2).

[figure not shown]
A face-to-face questionnaire should be conducted on the enrolled patients and baseline information such as, medical history, clinical assessment information, medication information, and living habits should be collected; and physical examination, UACR tests and funduscopy were performed on the patients. For outpatients, it is also necessary to query all the medical records of the enrolled patients on the day after the day of enrollment to supplement any missing information.

To evaluate the doctor's attention to chronic kidney disease, this study mainly reviewed the doctor's order to observe whether the doctor prescribes the UACR checklist for patients with T2DM to monitor the renal function of the patients. If the doctor has issued a UACR test for the patient, record the inspection value; if the doctor has not prescribed the test, use the

UACR measurement equipment provided in this study to obtain the results. When all the research-related information of the enrolled patients is collected, and the UACR results are obtained and fed back to the doctors, the data collection process is deemed to be over. In addition, after the doctor obtains the results of the UACR examination, whether to revise the doctor's order based on the detected nephropathy is also one of the ways to measure the doctor's awareness of the identification and management of the nephropathy of diabetic patients in the cardiology department.

Flowchart 1, Outpatient enrollment process

Flowchart 2, Inpatient enrollment process

5 Research evaluation

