4.1 Study data collection plan

The PLACARD study will be a cross-sectional observational study that collect patient information only once after screening and retrace the case system after the first visit, without any follow-up. It is expected that each center will complete the screening and

enrollment of patients within one month.

During the information collection period the investigator will:

1. Sign the informed consent form: Before signing the informed consent form, the participants should be fully informed of the research purpose and how the data will be used, and the researcher should also sign the informed consent form. The investigator and the patient each keep an original signed informed consent form;

2. Patient screening form: After signing the informed consent form, it will be confirmed whether the patient meets all the inclusion criteria and not all exclusion criteria, and the screening information will be recorded in the patient screening form. In order to ensure the continuity of screening, the screening information of potential patients who failed to enroll will also be recorded in the patient screening form;

3. After the patients are enrolled, the researchers should complete the following tasks and collect relevant data:

- Demographic information: gender, date of birth, education, type of medical insurance;
- Patient history: T2DM, hypertension, hyperlipidemia, coronary heart disease, atrial fibrillation, heart failure, stroke (ischemic and hemorrhagic), transient ischemic attack (TIA), cataracts, and macular degeneration;
- History of surgical intervention: coronary intervention, coronary artery bypass grafting and coronary angiographic stenosis;
- Questionnaire: Edinburgh Intermittent Claudication Questionnaire (ECQ) ;
- Physical examination: blood pressure, heart rate, height and weight;
- Clinical assessment information: blood glucose (including HbA1c , fasting blood glucose,

two-hour postprandial blood glucose), renal function (including serum creatinine glomerular filtration rate, UACR), blood lipids (including total cholesterol, LDL cholesterol, HDL Cholesterol, triglycerides), funduscopy, and the detection frequency of the above inspections in the past year (mainly based on patient self-report);

- Whether the doctor prescribes urine routine examination for inpatients, and whether the doctor issues a new doctor's order after the outpatients report back the renal function examination;

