- Combined drug information: this prescription drug and commonly used drugs (outpatients) and medications during hospitalization (inpatients);
- Information about patient behavior: smoking history and drinking history;
- UACR value detected on the day of enrollment;
- The result of funduscopy gained on the day of enrollment.

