5.2 Medical record inquiry

The indicators examined will be retraced by querying the HIS electronic medical record system. The medical records will be queried for the most recent transcripts of relevant tests such as blood glucose, lipids, blood tests and renal function of the enrolled patients in the last three months, to check for logical matches of disease or medication history, and combined with the patient's self-reported record of the frequency with which he/she has

monitored and managed the indicators in the past year.

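### Attention to CKD is judged mainly by whether a UACR is ordered at the index visit or stay, ignoring recent testing, so it can be understated by an unknown amount

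*Protocol*

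**What the plan says.** Protocol section 4.3 sets out how the doctor's attention to chronic kidney disease is evaluated: "this study mainly reviewed the doctor's order to observe whether the doctor prescribes the UACR checklist for patients with T2DM". Two branches follow. The first reads "If the doctor has issued a UACR test for the patient, record the inspection value". The second begins "if the doctor has not prescribed the test, use the" and goes on to the measuring device supplied by the study. No third branch covers a patient who was tested recently and for whom no new order was written.

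Section 4.1 makes the study a single contact: "collect patient information only once after screening and retrace the case system after the first visit, without any follow-up". Among the items collected is the "UACR value detected on the day of enrollment".

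Prior testing is collected in two other places. Section 4.1 asks for "the detection frequency of the above inspections in the past year (mainly based on patient self-report", and UACR is named there under renal function. Section 5.2 retrieves from the hospital records results for "blood glucose, lipids, blood tests and renal function of the enrolled patients in the last three months". Neither section links these data to the attention measure.

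Sections 4.3 and 5.4 add a second indicator: whether the doctor changes orders, diagnosis or prescription once the UACR result is known.

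**The concern.** Whether a test is ordered on a given occasion depends on two things: whether the doctor attends to kidney disease, and whether the patient was tested recently enough that no new order seemed needed. Section 4.3 reads the first from the order alone. A doctor who tested a patient a month ago and orders nothing today is then not distinguished from a doctor who has never tested that patient.

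Two consequences follow. The all-patient order rate can understate attention. It can also rank clinics wrongly, because a clinic that tested more of its patients earlier has fewer left to order for. A low order rate could then be published as evidence of poor awareness when part of it reflects testing already done. The prevalence of albuminuria is not at stake, since every patient without an ordered test is measured with the study device.

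**Working it through.** **Reading the text.** The words of the first branch in 4.3 do not say whether an earlier order counts. Section 4.1, however, requires a value from the day of enrollment and a single collection of information. Last month's result cannot supply that value. Without a new order, such a patient goes to the study device and so falls on the not-prescribed side. This follows from reading 4.1 and 4.3 together; no explicit scoring rule is stated.

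**The plan's own figure.** There is none for this measure. The only precision calculation (section 6.6) concerns prevalence and has no bearing here.

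**Inputs not in the protocol, assumed over a range:** visits per year v (1 to 12), share tested recently r (0 to 0.70), and order rate q among patients not recently tested (0.1 to 0.8). Two values of r, 0.351 and 0.041, borrow the UACR testing rates quoted in section 1.3 for diabetes and hypertension. Those come from an international cohort, not from these clinics.

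**Model 1, visit frequency (outpatients).** Suppose every patient is tested once a year and makes v visits. The share with an order at the index visit is 1/v, against true attention of 1, so the understatement is v-fold:
- v = 1: 100%, 1-fold
- v = 2: 50%, 2-fold
- v = 4: 25%, 4-fold
- v = 12: 8.3%, 12-fold

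Half the sample are inpatients (50 of 100 per center). If they are unaffected, the overall fold is 1/(0.5 + 0.5/v), which gives 1.0, 1.33, 1.6 and 1.85 for v = 1, 2, 4 and 12.

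**Model 2, recent testing.** Suppose recently tested patients get no new order. The all-patient order rate is (1 − r)q, the share monitored is r + (1 − r)q, and the fold is their ratio:

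| r | q = 0.1 | q = 0.5 | q = 0.8 |
|---|---|---|---|
| 0 | 1.0 | 1.0 | 1.0 |
| 0.041 | 1.43 | 1.09 | 1.05 |
| 0.10 | 2.11 | 1.22 | 1.14 |
| 0.351 | 6.41 | 2.08 | 1.68 |
| 0.70 | 24.33 | 5.67 | 3.92 |

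If instead the target is the order rate among patients without a recent test, the fold is q/[(1 − r)q] = 1/(1 − r): 1.00, 1.11, 1.54 and 3.33 at r = 0, 0.10, 0.351 and 0.70.

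**Ranking.** Take two clinics with the same q = 0.5. With r = 0.10 the all-patient order rate is 0.90 × 0.5 = 45% and the share monitored is 0.10 + 0.45 = 55%. With r = 0.50 the figures are 0.50 × 0.5 = 25% and 0.50 + 0.25 = 75%. The clinic that monitors more shows the lower order rate.

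**The case against.** The strongest reply is that the data needed to separate recently tested patients are already planned, and that denominators and restrictions are usually set in a statistical analysis plan, which is not shown here. This stands in part. Past-year frequency and three-month records are collected, which is why the fix is cheap. But the protocol itself defines the attention measure and sets the reach of the record query, and an analysis plan cannot recover records that were never retrieved. A test 4 to 12 months back is known mainly from the patient's recall.

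It can also be said that 4.3 calls order review the main measure, not the only one. That is so. The second indicator, however, shows how a doctor reacts to a result that the study may itself have supplied, not whether the doctor was already monitoring.

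Further, the order rate is not named among the endpoints in section 6, and no comparison of order rates between settings or hospital levels is specified. Both points stand and limit the weight of the concern. So does the point that arithmetic per visit does not fit inpatients.

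A reader might infer that attention is understated several-fold, for instance that full attention would be reported as 8% to 25%. The protocol does not support this. Those figures need every patient to be tested yearly and seen 12 or 4 times a year. Nor does the protocol state outright that recently tested patients are scored as missed.

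**Conclusion.** The concern holds as a matter of definition and direction, not of size. If recently tested patients without a new order fall on the not-prescribed side, as sections 4.1 and 4.3 together imply, the all-patient order rate lies at or below true attention. The amount cannot be computed from the protocol. Under the assumed inputs it runs from none (r = 0, or one visit a year) to more than tenfold where many patients were tested recently and few of the rest are ordered. Under the yearly-testing model it stays below twofold overall if inpatients are unaffected. These results assume that recently tested patients are not re-ordered; any re-ordering shrinks the gap. The effect falls mainly on outpatients. It leaves the primary prevalence endpoint untouched and concerns a measure outside the listed endpoints. It is worth correcting because, as written, the order rate cannot be read as attention and the remedy uses data already planned.

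**What to change.** In section 4.3, state whether an order written before the index visit or stay counts, and classify each patient as:

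1. UACR tested within the past year;
2. not tested in that window, and ordered now;
3. neither.

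Report the order rate among patients without a past-year test, (2)/[(2)+(3)], and the share monitored, (1)+(2) over all patients. Show both separately for outpatients and inpatients. Do not present the all-patient order rate alone as attention or awareness. The past-year window is the recall period that section 4.1 already uses; it is not offered as a testing schedule.

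The source for class 1 is the past-year frequency in section 4.1, supported by the three-month record query in section 5.2. The case report form should record that frequency for UACR on its own, not for renal function as a group.

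Cost: a wording change in 4.3 and two extra tabulations. The downside is that class 1 rests mainly on self-report. Extending the record query from three to 12 months for UACR would reduce that reliance; it is a modest change to data collection, but across 30 centers, and it would still miss tests done at other hospitals. Class 1 also shows that the patient was tested, not which doctor ordered the test, and the report should say so.
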